### 1 Scope

This document details the testing plan to determine the clinical performance of the Q-POC SARS-CoV-2 Assay (Q27001) in accordance with FDA requirements.

 www.quantumdx.com	Review Period	Doc. ID	Version
Document Title: Q-POC SARS-CoV-2 Assay (Q27001) Clinical Performance Study Plan	1 year	QVTP-39	1.0

## 2 Referenced Documents

Document ID	Title
QQA-8	Document Control Procedure
QTEM-270	Deviation Record Template Form
QQA-14	Control of non-conforming product

## 3 Device Intended Use

The Q-POC SARS-CoV-2 Assay is a real-time PCR test intended for use on the Q-POC instrument for the qualitative detection of nucleic acids from Severe Acute Respiratory Syndrome Coronavirus 2 (SARS-CoV-2), in nasal mid-turbinate swabs (MTSW) obtained from individuals suspected of COVID-19 by their healthcare provider. Testing is limited to laboratories certified under the Clinical Laboratory Improvement Amendments of 1988 (CLIA), 42 U.S.C. §263a, that meet requirements to perform high complexity or moderate complexity tests.

Results are for the detection of SARS-CoV-2 RNA. SARS-CoV-2 RNA is generally detectable in nasal mid-turbinate swabs (MTSW) during the acute phase of infection. Positive results are indicative of the presence of SARS-CoV-2 and aids in the diagnosis of COVID-19 if used in conjunction with other clinical and epidemiological information. Positive results do not rule out bacterial infection or co-infection with other viruses.

Negative results do not preclude SARS-CoV-2 infection and should not be used as the sole basis for patient management decisions. Negative results must be combined with clinical observations, patient history, recent exposures and epidemiological information. Laboratories within the United States and its territories are required to report all results to the appropriate public health authorities.

The Q-POC SARS-CoV-2 Assay is intended for use by laboratory personnel who have received specific training on the use of the Q-POC SARS-CoV-2 Assay in conjunction with the Q-POC instrument (Q29001).

## 7 Study Synopsis

Title	Q-POC SARS-CoV-2 Assay Clinical Performance Study Plan
Primary Objective	To evaluate the clinical diagnostic performance (positive percent agreement [PPA] and negative percent agreement [NPA]) of QuantuMDx's Q-POC SARS-CoV-2 Assay when running mid-turbinate nasal swab (MTSW; also known as nasal mid-turbinate, NMT) compared to Roche Cobas 6800 SARS-CoV-2 Comparator Test.
Study Design	
Prospective clinical study enrolling patients with signs and symptoms that are consistent with SARS-CoV-2. Positive and negative specimens will be run on the Q-POC SARS-CoV-2 Assay in comparison with an FDA-approved reference standard. The reference standard will be the Roche Cobas 6800 SARS-CoV-2.
 
Three clinical testing sites, located in different geographical locations of the U.S., will be used to collect SARS-CoV-2 positive and negative specimens. Testing sites may be independent from sample collection sites – i.e., there can be multiple sample specimen collection sites that feed into the three testing sites.

Study Population	
Prospectively enrolled patients >18 years of age with signs and symptoms that are indicative of SARS-CoV-2 infection.
 
Subject populations must be from the U.S. to be representative of the intended patient population(s).

 www.quantumdx.com	Review Period	Doc. ID	Version
Document Title: Q-POC SARS-CoV-2 Assay (Q27001) Clinical Performance Study Plan	1 year	QVTP-39	1.0

Intended Sample Type	Nasal mid-turbinate swab specimens (MTSW)
Sample Size	Nasal mid-turbinate swab (MTSW) swab samples from sufficient participants to achieve a minimum target at the end of the study of:  50 comparator test-confirmed SARS-CoV-2 positive samples  500 comparator test-confirmed SARS-CoV-2 negative samples.
Eligibility Criteria	Inclusion Criteria  Participants must:  Be over the age of 18 years.  Present with symptoms indicative of SARS-CoV-2 infection, within 0-5 days of symptom onset.  Have capacity to give informed consent.  Exclusion Criteria  Under the age of 18.  No symptoms of SARS-CoV-2 infection.  Lack of capacity to give informed consent.
Study Duration	The study period will start on 07NOV22 and will continue until sample collection is complete.
Study Personnel	The study should include 1-3 operators at each of 3 sites to run Q-POC tests.  Trained professionals at clinical diagnostic testing sites will collect the specimens and run the comparator test.

## 8 Objectives of the Clinical Performance Study

To evaluate the clinical diagnostic performance (PPA and NPA) of QuantuMDx's Q-POC SARS-CoV-2 Assay when compared to the Roche Cobas 6800 SARS-CoV-2 in compliance with FDA requirements.

 www.quantumdx.com	Review Period	Doc. ID	Version
Document Title: Q-POC SARS-CoV-2 Assay (Q27001) Clinical Performance Study Plan	1 year	QVTP-39	1.0

## 9 IVD Medical Device Under Investigation and Comparator(s)

*Table 1: Information on the IVD Medical Device Under Investigation*

Device Under Test	Manufacturer	Product Number
Q-POC	QuantuMDx Group Ltd	Q29001
Q-POC SARS-CoV-2 Assay	QuantuMDx Group Ltd	Q27001

*Table 2: Information on the comparator assay*

Comparator Device	Manufacturer	Product Number
Roche cobas SARS-CoV-2 (Assay for 6800)	Roche	SARS-CoV-2-192T P/N: 09175431190, cobas® SARS-CoV-2-480T P/N: 09343733190
cobas® SARS-CoV-2 Control Kit	Roche	P/N: 09175440190
cobas® 6800/8800 Buffer Negative Control Kit	Roche	P/N: 07002238190
Roche cobas 6800 system	Roche	P/N: 05524245001

## 10 Testing Sites

The study will be conducted at three external collection and testing sites located in the U.S. (in different geographical locations).

Testing sites may be independent from sample collection sites – i.e., there can be multiple sample collection sites that feed into the three testing sites. If some non-U.S. testing/collection sites are chosen, the relevance of this patient population to a U.S. population will be documented.

## 11 Operators

The study will include 1-3 operators at each site and at least nine (9) operators across all sites. The operator study participants enrolled must represent anticipated operators of the Q-POC SARS-CoV-2 Assay within the use-case environment. They should be laboratory personnel who

QuantuMDx www.quantumdx.com	Review Period	Doc. ID	Version
Document Title: Q-POC SARS-CoV-2 Assay (Q27001) Clinical Performance Study Plan	1 year	QVTP-39	1.0

have received specific training on the use of the Q-POC SARS-CoV-2 Assay in conjunction with the Q-POC instrument (Q29001). Operators must be suitably trained to work in laboratories certified under the Clinical Laboratory Improvement Amendments of 1988 (CLIA), 42 U.S.C. §263a, that meet requirements to perform high complexity or moderate complexity tests.

Operators should be personnel currently employed in the selected intended use sites and testing should be integrated into the daily workflow of the facility.

Education (including experience and training) and the occupation of each operator will be recorded and tabulated for each operator enrolled in the study. Study sites will be required to provide CVs and a filled in information form for potential operators prior to approval for their inclusion in the study. This will ensure that the participants meet the definition of intended operators.

The operators who participate in the study will be provided with the test kit in the form that will be made available in the actual intended use settings when the test is marketed. The operators should also be provided with the instructions for use and the training that is intended for such operators.

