## 12.3 Inclusion and Exclusion Criteria

### Inclusion Criteria:

Participants must:

- Be over the age of 18 years.
- Present with any symptoms indicative of SARS-CoV-2 infection within 0 to 5 days of symptom onset.

QuantuMDx www.quantumdx.com	Review Period	Doc. ID	Version
Document Title: Q-POC SARS-CoV-2 Assay (Q27001) Clinical Performance Study Plan	1 year	QVTP-39	1.0

- Have capacity to give informed consent.

Exclusion Criteria:

Participants must not:

- Be under the age of 18.
- Have no symptoms indicative of SARS-CoV-2 infection.
- Lack capacity to give informed consent.

Required patient and sample data to be recorded:

- Collection testing date and time
- Age
- Sex
- Country of residence
- Ethnicity
- Clinical signs and symptoms
- Time since onset of symptoms
- Clinical history
- Co-morbidities
- Medications taken or administered
- Vaccination status (SARS-CoV-2 and Influenza)
- Other relevant diagnostic data e.g., indications for testing
- Time taken between specimen collection and sample processing on Q-POC

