## 12.4 Number of Specimens

Nasal mid-turbinate swab (MTSW) samples from sufficient participants to achieve a minimum target at the end of the study of:

- 50 comparator test-confirmed SARS-CoV-2 positive samples
- 500 comparator test-confirmed SARS-CoV-2 negative samples

Sample numbers chosen are in alignment with FDA recommendations in response to QuantuMDx's pre-submission Q220638.

QuantuMDx www.quantumdx.com	Review Period	Doc. ID	Version
Document Title: Q-POC SARS-CoV-2 Assay (Q27001) Clinical Performance Study Plan	1 year	QVTP-39	1.0

An adequate number of subjects (N=550) will be enrolled to achieve a minimum 50 symptomatic positive and 500 negative cases confirmed via Roche Cobas 6800 SARS-CoV-2, a FDA approved reference standard.

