## 15 Statistical Considerations

The diagnostic performance of the Q-POC SARS-CoV-2 Assay (in terms of PPA and NPA) will be determined using the Roche Cobas 6800 SARS-CoV-2 Test, as an FDA-approved reference standard comparator assay. This will be done for the entire dataset and also for subsets classified by comparator Ct-banding ( $Ct \leq 25$ ,  $25 < Ct \leq 30$ ,  $Ct > 30$ ) for SARS-CoV-2. Diagnostic performance will be assessed as follows:

- Positive Percent Agreement (PPA) will be calculated as  $100\% \times (TP / (TP + FN))$ .
- Negative Percent Agreement (NPA) will be calculated as  $100\% \times (TN / (TN + FP))$ .
- PPA and NPA will include 95% CI.

Where:

- True Positive (TP) indicates that both the Q-POC SARS-CoV-2 Assay and comparator assay returned a positive result for the target.
- False Negative (FN) indicates that the Q-POC SARS-CoV-2 Assay returned a negative result for the target, while the comparator assay returned a positive result.
- True Negative (TN) indicates that both the Q-POC SARS-CoV-2 Assay and comparator assay returned a negative result for the target.
- False Positive (FP) indicates that the Q-POC SARS-CoV-2 Assay returned a positive result for the target, while the comparator assay returned a negative result.

The performance of the Q-POC SARS-CoV-2 Assay will be presented based on the overall study (all specimens of a claimed specimen type combined) as well as stratified by site and time since symptom onset.

QuantuMDx www.quantumdx.com	Review Period	Doc. ID	Version
Document Title: Q-POC SARS-CoV-2 Assay (Q27001) Clinical Performance Study Plan	1 year	QVTP-39	1.0

The rate of invalid/indeterminate results observed during the clinical study by site and overall will be reported. The prevalence of infection observed at each clinical site as determined by the comparator and the detection rate by the Q-POC SARS-CoV-2 Assay separately will be reported.

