## 17 Accountability of the IVD Medical Devices under Investigation

Access to IVD medical devices under investigation shall be controlled and these devices shall be used only in the clinical performance study according to this Clinical Performance Study Plan (QVTP-39).

The sponsor shall keep records to document the physical location of all IVD medical devices under investigation from shipment of the devices to the study site until return or disposal.

The principal investigator or an authorized designee shall keep records documenting the receipt, use, return and disposal of the IVD medical devices under investigation, which shall include, when applicable:

- a) The date of receipt
- b) The identification of each Q-POC instrument via serial number and Q-POC SARS-CoV-2 Assay Test cassettes via batch number
- c) The expiry date of the Q-POC SARS-CoV-2 Assay Test Cassettes
- d) The dates of use
- e) The date on which the devices under investigation were returned or disposed of
- f) The date of return of unused, expired or malfunctioning devices under investigation

QuantuMDx www.quantumdx.com	Review Period	Doc. ID	Version
Document Title: Q-POC SARS-CoV-2 Assay (Q27001) Clinical Performance Study Plan	1 year	QVTP-39	1.0

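### Is the nine-operator requirement empty because the plan ties no Q-POC run to an operator?

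*Combined protocol and SAP*

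**What the plan says.** Section 11 (Operators) sets the staffing: "The study will include 1-3 operators at each site and at least nine (9) operators across all sites". The Synopsis in section 7 gives only the per-site range: "The study should include 1-3 operators at each of 3 sites to run Q-POC tests". Section 10 fixes the number of sites: "The study will be conducted at three external collection and testing sites located in the U.S".

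On what is known about operators, section 11 says: "Education (including experience and training) and the occupation of each operator will be recorded and tabulated for each operator enrolled in the study". It also requires that they be trained laboratory staff already employed at the site, that CVs and an information form be supplied before an operator is approved, and that testing be part of the facility's ordinary work. It presents the CV and form check as the means of making sure that operators fit the intended-user definition.

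The required patient and sample data in section 12.3 name no operator; the last item is "Time taken between specimen collection and sample processing on Q-POC". The device records in section 17 include "The identification of each Q-POC instrument via serial number and Q-POC SARS-CoV-2 Assay Test cassettes via batch number", with dates of use, but not who ran the test. Section 15 reports agreement overall, by comparator Ct band, by site and by time since symptom onset. On failed runs it says: "The rate of invalid/indeterminate results observed during the clinical study by site and overall will be reported". Section 12.4 gives the size of the study: "An adequate number of subjects (N=550) will be enrolled to achieve a minimum 50 symptomatic positive and 500 negative cases".

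**The concern.** Two things catch the eye. The first is arithmetical: a range of one to three per site sits awkwardly beside a total of nine at three sites, because only the top of the range reaches it. A site that reads the Synopsis alone could staff with one or two operators and cause section 11 to be missed.

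The second is about evidence. A requirement for nine operators looks intended to show that the assay works in several hands. If the plan does not link runs to operators, sets no minimum number of runs and tabulates no result by operator, nine could be listed while three do nearly all the testing. Operator identity that is not captured at the time of the run cannot be rebuilt from the data items the plan lists. A poor performer could then be hidden inside a site's invalid or discordant rate. What would be at stake is the claim that the results come from a spread of intended users; the calculation of PPA and NPA is not in question.

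**Working it through.** **Inputs.** Three testing sites (section 10); one to three operators per site and at least nine overall (section 11); 550 subjects, 50 positive and 500 negative by the comparator (section 12.4). One Q-POC run per subject is taken, before any repeats. The documents give no workload split and no expected invalid rate, so every split and rate below is an assumption.

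**Reproducing the nine.** The maximum is 3 sites × 3 operators = 9, which equals the stated minimum. Of the 3 × 3 × 3 = 27 possible staffing patterns, totals run from 3 to 9 and only one pattern reaches 9. The requirement is tight but can be met, and the Synopsis range does not contradict it.

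**How uneven the split could be.** An even split gives 550/9 = 61.1 runs, 50/9 = 5.6 positives and 500/9 = 55.6 negatives per operator. At the extreme, six operators run one test each, so the other three run 550 − 6 = 544, or 544/550 = 98.9%.

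The effective number of operators is (Σn)²/Σn². With runs of 181, 181, 182 and six ones, this is 550²/(181² + 181² + 182² + 6) = 302,500/98,652 = 3.07. For less extreme cases, let the lead operator at each of three equal sites take share s, with the other two sharing the rest equally. Then the effective number is 1/{3[(s/3)² + 2((1 − s)/6)²]}:

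| Lead share s | Effective operators |
|---|---|
| 1/3 | 9.0 |
| 0.6 | 6.8 |
| 0.8 | 4.5 |
| 0.9 | 3.7 |

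So the text does permit concentration. Whether that breaches anything depends on whether the plan promises a spread of workload. It does not: section 11 defines suitable operators by training, employment and approval.

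**What agreement by operator would show.** For n of n agreements, the exact lower 95% limit is 0.025^(1/n). Even with an equal split:

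- 6 of 6 positives: 0.025^(1/6) = 0.54, so 54% to 100%.
- 56 of 56 negatives: 0.025^(1/56) = 0.94, so 94% to 100%.

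A PPA by operator with a lower limit of 54% under perfect agreement cannot separate a good operator from a poor one.

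**Would the site rate hide a weak operator?** Assume invalid rates of 2%, 2% and 15% for three operators with 61.1 runs each. The site expects 61.1 × 0.19 = 11.6 invalid runs in 183.3, or 6.3%. A site with all three operators at 2% expects 183.3 × 0.02 = 3.7. The planned report by site would show roughly a threefold difference. It would not name the operator, but it would give the monitor reason to ask.

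**Is the identity really unrecorded?** The list in section 12.3 covers patient and sample data, where an operator field need not appear. The list in section 17 concerns device accountability; it is not a record of runs, and it does not tie serial or batch numbers to individual results either. Section 14 provides for case report forms checked against source documents and for collection of test outputs, without itemising either. The visible text therefore does not require the field, but does not show that it is absent. The part of the plan between sections 3 and 7 was not available for this check.

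**The case for a change.** The strongest case for a change is that it costs almost nothing and cannot be made good later. CVs and occupations show who was enrolled, not who produced the data. If workloads are skewed, pooled PPA and NPA mainly describe a few people, and a reader of the report could not tell. The plan tracks instruments and cassette batches and reports invalid runs by site, yet leaves out operator, an obvious source of variation between runs. One coded field and one descriptive table would close the gap without extra specimens or staff.

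Much of this stands as good practice. A run log with an operator code would help to trace a cluster of invalid runs, and the Synopsis would read better with the total of nine beside the range. What does not stand is the step from there to a defect. Calling the nine nominal presupposes a workload rule that the plan never states. Testing within the ordinary work of a laboratory may well fall mostly to one person per site, and that would then be representative use. A minimum number of runs per operator could pull against that aim. The illustrative shares and invalid rates are assumptions, and no stated objective concerns performance by operator.

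**Conclusion.** No change to the plan is needed. The figure of nine reproduces and is met by three operators at each of three sites; the mismatch with the Synopsis is a matter of tidying, since the two statements are compatible. The visible text does not require operator identity on each run and would allow three people to perform up to 98.9% of runs when six others do one each. But it makes no promise about workload, and its check on representativeness rests on who the operators are. PPA, NPA, their confidence intervals as planned and the 50/500 targets are all computed without operator, and agreement by operator would be too imprecise to interpret (54% to 100% for 6 of 6). An operator code and a count of runs and invalid results by operator would be a sensible optional addition, and study staff may already capture the code on the case report form. This conclusion rests on one run per subject before repeats, on reading the three sites as the testing sites, and on the study's objective remaining overall agreement with the comparator.

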## 12 Specimen Information

### 12.1 Specimen Type to be Tested

*Table 3: Claimed specimen type to be validated in this Clinical Performance Study Plan (QVTP-39)*

Anatomical Location/Sample type	Common/Uncommon Respiratory Sample Type	Diluted into Liquid?	Type of Liquid/Transport medium
Mid-turbinate nasal swab (MTSW)	Common	Yes	MSwab preservation medium

The comparator test, Roche Cobas 6800 SARS-CoV-2 Test is validated for testing nasopharyngeal swab samples (NPS); therefore, an additional set of this specimen type will be collected for the comparator test in Copan UTM.

Sample Categories:

- Category I: Fresh samples, prospectively collected and tested in an 'all comers' fashion.
- Category II: Archived samples prospectively collected, frozen, and retrospectively tested. All samples are collected and tested in an 'all comers' fashion.

[figure not shown]
 www.quantumdx.com	Review Period	Doc. ID	Version
Document Title: Q-POC SARS-CoV-2 Assay (Q27001) Clinical Performance Study Plan	1 year	QVTP-39	1.0

Ideally, Category II samples should be limited to no more than 30% of the total prospective samples enrolled in the clinical study.

[figure not shown]
Please note that Category I and II samples must be collected sequentially from all patients meeting study inclusion criteria and representing the assay's intended use population (i.e., not pre-selected) presenting at a clinical facility between two pre-determined dates. This minimizes bias and prevalence of infection in the population can be evaluated. The Category II samples should be appropriately stored (e.g., frozen at -70°C to -80°C).

It is anticipated that within this clinical study both the comparator and candidate samples will be tested under the Category I conditions.

## 12.2 Method of Specimen Collection

1. Open the kit package and remove the tube of MSwab™ reagent and the inner pouch containing the sterile swab applicator.

2. Remove the swab applicator from its peel pouch and use it to collect the clinical specimen.

 www.quantumdx.com		Review Period	Doc. ID	Version
Document Title: Q-POC SARS-CoV-2 Assay (Q27001) Clinical Performance Study Plan	1 year	QVTP-39	1.0	

[figure not shown]
- Using gentle rotation and tilting patient's head back 70 degrees, insert the swab about 2 cm into the nostril without tipping the swab head up or down.

 The nasal passage runs parallel to the floor, not parallel to the bridge of the nose.

- Leave the swab in place for a few seconds, then slowly rotate the swab as it is being withdrawn.

 **DO NOT USE FORCE** while inserting the swab. It should travel smoothly with minimal resistance. If resistance is encountered, withdraw the swab a little bit, without taking it out of the nostril, then elevate the back of the swab and move it forward.

At all times when handling the swab applicator, the operator must **NOT** touch the area below the breakpoint line, as this may result in contamination.

- Unscrew the cap of the MSwab™ tube and insert the swab until the marked breaking point.
- Bend and break the swab at the marked breaking point holding the tube away from your face.

 Hold the tube away from your face while breaking the swab handle to prevent potential exposure to biological material.

 **DO NOT** place the swab on a bench. Use of aseptic technique is recommended to avoid contamination.

- Discard the broken handle into an approved biohazard disposable container.
- Replace cap on the tube and secure tight to prevent leaks.
- Invert the tube five (5) times.

